## 6.3 General Statistical Procedures

### 6.3.1 Overview

Data from Site Investigators and study Subjects will be treated separately, and combined into one dataset, based on the study assessments of interest. Validated instruments will be scored according to developer guidelines, reporting domain scores and overall summary scores, as appropriate. Home-grown questions/items will be analyzed and reported individually, based on the respective response scales. Change from Baseline (CFB) in scores (for continuous variables) or proportions (for discrete variables) will be computed as Week-12 minus Baseline measure for respective question responses.

Discrete measures will be assessed using summary statistics encompassing percentage of Subjects reporting particular outcome measures. The statistical differences in discrete variables to compare different patient groups (for subgroup analysis) for a given measure at a particular timepoint (such as Baseline or Week-12), or CFB in proportion of patients reporting a particular response to an outcome measure at a particular timepoint (such as Week-12) will be assessed using a  $\chi^2$  test. In case of likert scales, to compute P-values for CFB in proportions, the top-two response categories (of a likert scale) for a given question at Baseline will be grouped together into a single group proportion (versus the rest of the population/responders all together) and compared to the same group proportion at Week-12; the procedure will be repeated for the bottom-two response categories (of a likert scale) for a given question, by grouping them together into a single group proportion and compare it to the same group proportion at Week-12. For example, for ASIS item # 1 (how oily is your face right now), proportion of patients reporting “Not at all/A little” at Baseline will be grouped together (vs. rest of the population/responders) and compared to proportion of patients reporting “Not at all/A little” at Week-12; similarly, proportion of patients reporting “Quite a bit/Very” at Baseline will be grouped together and compared to proportion of

patients reporting “Quite a bit/Very” at Week-12, to compute respective P values. Continuous measures will be assessed using summary statistics; paired sample t-tests will be used to assess statistical differences for CFB evaluations, while independent sample t-tests will be used to assess statistical differences between different patient groups (for subgroup analysis) for a given measure at a particular timepoint (such as Baseline or Week-12).

Computation of statistical differences will be performed only as an exploratory step (and not for hypothesis testing), considering the descriptive nature of the study; for such exploratory evaluation, P value  $\leq 0.05$  will be considered significant. All statistical analyses will be based on all available data assuming that all missing data are uninformative and will be conducted using appropriate statistical software, such as SAS.

An interim analysis will be conducted using FAS, upon completion of 12 weeks of data collection (from both patients and clinicians) for ~200 study Subjects, using the statistical methods identical to the analyses planned for FAS-based final data analyses; the focus of the interim analyses will be the primary objective, secondary objective and select additional objectives, as outlined below; no subgroup analyses will be considered.

- FAS cohort demographics
- PROs: Antibiotic attitudes at baseline
- PROs: CFB in EPQ measures
- PROs: CFB in ASIS measures
- PROs: CFB in Patient Acne Severity and How Face Looks (with and without LOCF imputation)
- PROs: CFB in Parent/caregiver concerns about the child with Acne:
  - Understanding child's concerns
  - Concerned about child's acne
  - Concerned about child's ability to accomplish future goals
- Facial IGA and Facial IGA success (with and without LOCF imputation)
- Select comparison of patient and clinician reported measures: Acne Severity (with LOCF imputation)

- Select comparison of pediatric patient and caregiver reported measures:
  - Understanding child's concerns
  - Concerned about child's acne
  - Concerned about child's ability to accomplish future goals
- Clinician satisfaction with sarecycline
- Sarecycline treatment characteristics

The description of the individual study measures are outlined in the forthcoming sections.

The final study analyses encompassing all study outcome measures will be conducted after the completion of 12 weeks of data collection for all study Subjects, data QC is completed, and upon final database lock.

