### **3.1 Subject Inclusion Criteria**

**Patient Inclusion Criteria:** In order to be eligible to participate in this study, an individual must meet all of the following criteria:

- Male or female, aged 9 years and above at the time of study recruitment.
- Has facial non-nodular AV with IGA score of moderate (3) or severe (4).
- Considered as a potential candidate for sarecycline treatment to manage their AV, per clinician's judgment.
- Able to read and write English.
- Provide consent (in case of adult patients) or assent (in case of pediatric patients) to participate in the study.
- Willing to comply with all study procedures and be available for the duration of the study.

**Caregiver Inclusion Criteria:** In order to be eligible to participate in this study, an individual must meet all of the following criteria:

- Male or female, aged 18 years and above.
- Able to read and write English.
- Primary caregiver of the study-eligible patient.
- Provide consent to participate in the study.
- Willing to comply with all study procedures and be available for the duration of the study.

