#### **6.6.4 CFB in PROs**

CFB in ASIS domain scores and subscale scores at Week 12 will be assessed (estimated as Week 12 score minus Baseline score). CFB will be first analyzed descriptively for the entire FAS cohort. For this analysis of domain scores, measures will be considered as continuous variables. No missing data imputation will be used. CFB in proportion of individuals reporting specific response for individual items of ASIS will be conducted by treating these variables as discrete variables, and grouping into top-2 or bottom-2 response scales (within the likert scale), as outlined in Section 6.3.1. Scoring, scaling, and the handling of missing data will be handled in accordance with the recommendations accompanying the ASIS documentation.

CFB in proportion of individuals reporting specific response for select individual items of ASIS, most specifically, items # 9 & 10, will be conducted by treating these variables as discrete variables, and grouping into top-2 or bottom-2 response scales (within the likert scale), as outlined in Section 6.3.1. CFB at Weeks 4 & 8 will be assessed in addition to Week 12. LOCF data imputation method will be used to impute responses to ASIS items # 9 & 10 for respective encounters for the Subjects with missing data at those encounters, prior to analyses. CFB for these two measures (with and without LOCF imputation) will be first analyzed descriptively for the entire cohort, and then analyzed for select subgroups (as outlined in Section 6.3.2) with measures that use LOCF imputation.

Items from EPQ will be analyzed individually and CFB in individual questions/items will be reported descriptively for relevant categories of responses (depending on the response scales). No missing data imputation will be undertaken for these items.

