## 7 DATA TABLES

All patients who received at least one dose of sarecycline during the study observation period and had at least some data pertaining to ASIS and EPQ items (related to primary research objective) at Week 12 will be included in **Full Analysis Set (FAS)** to facilitate the planned descriptive analysis. Correspondingly, patients who completed the study survey at Week 12 will be included in FAS, since patients answering Week 12 survey will have completed all relevant PRO related questions.

Safety data analyses will be conducted among the Safety Population, that correspond to the entire study cohort that took at least one does of sarecycline. Correspondingly, all patients completing the baseline survey and took at least one dose of sarecycline, amounting to N=300 will be included in this analysis.

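### SAP 6.3.1 tests within-patient changes in proportions with an unpaired chi-square test, and the IGA change-from-baseline p-values are uninformative because eligibility fixes the baseline

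*SAP*

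**What the plan says.** SAP section 3 describes a single-arm cohort in which the same patients are surveyed at baseline and at Weeks 4, 8 and 12. Section 6.3.1 (Overview) sets the tests.

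- **Proportions.** One sentence names chi-square both for differences between patient groups and for change from baseline, the latter in the words "CFB in proportion of patients reporting a particular response to an outcome measure at a particular timepoint (such as Week-12) will be assessed using a" (the sentence then ends with the name of that test). For Likert items, the two highest or two lowest categories at baseline are "grouped together into a single group proportion (versus the rest of the population/responders all together) and compared to the same group proportion at Week-12".
- **Means.** Here the SAP does separate the two cases: "paired sample t-tests will be used to assess statistical differences for CFB evaluations", and independent-sample t-tests are kept for subgroups.
- **Status.** "Computation of statistical differences will be performed only as an exploratory step (and not for hypothesis testing"), yet P ≤ 0.05 is still to be called significant.
- **Interim.** The analysis at about 200 subjects is run "using the statistical methods identical to the analyses planned for FAS-based final data analyses".

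Section 6.6.4 extends the grouped-proportion method for ASIS items 9 and 10: "CFB at Weeks 4 & 8 will be assessed in addition to Week 12". Section 3.1 requires that each patient "Has facial non-nodular AV with IGA score of moderate (3) or severe (4"). Tables 7.2.4.2 and 7.2.4.6 nevertheless plan p-values for change from baseline in the IGA clear/almost-clear and moderate/severe proportions at Weeks 4, 8 and 12. Table 7.2.4.5 plans subgroup p-values for the clear/almost-clear proportion at baseline.

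No paired test for proportions is named anywhere in the SAP. Protocol 12.3.1 likewise names only chi-square for discrete variables. The optional repeated-measures analyses in Protocol 12.3.3 are not carried into the SAP.

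**The concern.** There are two separate problems.

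**Unpaired test on paired data.** A chi-square test on two marginal proportions treats the baseline and follow-up answers as coming from different people. Its variance leaves out the within-patient covariance, so the nominal 0.05 is not the actual level. The rule governs the change-from-baseline p-values for EPQ items, individual ASIS items, ASIS items 9 and 10 over time, and caregiver items (Tables 7.1.6.2, 7.1.9, 7.1.13, 7.1.15 and 7.1.18). These are the item-level results for the PROs that form the primary endpoint. What is at stake is the significance label: a modest real improvement could be reported as non-significant.

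**IGA tested against a baseline fixed by design.** Eligibility forces 0% clear/almost clear and 100% moderate/severe at baseline, apart from eligibility deviations. Change can go only one way, so the p-value asks only whether anyone improved. No choice of test repairs this.

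Not affected: the estimated proportions and changes, the ASIS domain and subscale changes (paired t-test, Table 7.1.10), and the IGA success endpoint, which has no baseline test.

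**Working it through.** The plan gives no power, effect size or correlation, so it has no figure to reproduce.

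**Inputs.** From the documents: significance threshold 0.05; interim n ≈ 200; at most 300 subjects; baseline IGA of 3 or 4. Assumed: within-patient correlation ρ of the binary answer from 0.1 to 0.5; n = 250 as a middle value; a 40% baseline proportion.

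**1. Number of p-values.** From the table shells: 7.1.6.2, 11 × 2 = 22; 7.1.9, 17 × 2 = 34; 7.1.13, 3 × 2 × 3 = 18; 7.1.15, 18; 7.1.18, 3 × 2 = 6. Total 98.

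**2. True level of the unpaired test.** With equal proportions p, the variance of the difference is 2p(1−p)(1−ρ)/n, but the test uses 2p(1−p)/n. The true level is therefore 2·(1 − Φ(1.96/√(1−ρ))), whatever n is:

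| ρ | 0.1 | 0.2 | 0.3 | 0.4 | 0.5 |
|---|---|---|---|---|---|
| True level | 0.039 | 0.028 | 0.019 | 0.011 | 0.006 |

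Simulation at n = 200 to 300 and ρ = 0.3 and 0.5 agrees (about 0.019 and 0.006). McNemar's test stays at 0.048 to 0.051 in the same settings. If ρ were negative the error would reverse (about 0.074 at ρ = −0.2).

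**3. Smallest change from 40% that reaches p ≤ 0.05.** Let p₁ be the baseline and p₂ the follow-up proportion, p̄ their mean, and π₁₁ = p₁p₂ + ρ√(p₁(1−p₁)p₂(1−p₂)).

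- Unpaired: z = (p₂−p₁)/√(2p̄(1−p̄)/n)
- McNemar: z = (p₂−p₁)√n/√(p₁+p₂−2π₁₁)

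| n | Unpaired (points) | McNemar, ρ = 0.1 to 0.5 (points) |
|---|---|---|
| 200 | 9.75 | 9.29 to 6.92 |
| 250 | 8.71 | 8.29 to 6.17 |
| 300 | 7.94 | 7.56 to 5.63 |

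**4. Worked example: 40% to 48%, ρ = 0.4.** Here π₁₁ = 0.192 + 0.4 × √(0.24 × 0.2496) = 0.2899, so the discordant fraction is 0.88 − 2 × 0.2899 = 0.3002. At n = 200 the unpaired z is 0.08/√(2 × 0.44 × 0.56/200) = 1.61 and the McNemar z is 0.08 × √200/√0.3002 = 2.07.

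| n | Unpaired p | McNemar p |
|---|---|---|
| 200 | 0.107 | 0.039 |
| 250 | 0.072 | 0.021 |
| 300 | 0.048 | 0.011 |

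The label differs at 200 and 250 but not at 300. Simulated power for this change at n = 250 is about 43% unpaired and 65% paired.

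**5. IGA against a baseline of 0 out of n.** With 4 improved patients, uncorrected chi-square gives p = 0.044 to 0.045 for n from 200 to 300. With 6, Fisher's exact test gives p = 0.030 and exact McNemar gives 2 × 0.5⁶ = 0.031. Four of 300 is 1.3%; six of 200 is 3.0%. The moderate/severe row mirrors this from 100%. Tables 7.2.4.2 and 7.2.4.6 hold 2 × 3 = 6 such p-values each, 12 in all. In the baseline column of Table 7.2.4.5 every cell is 0%, so the expected counts are zero and chi-square is undefined.

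**The case against.** McNemar's statistic is itself referred to a chi-square distribution, and the t-tests for change are paired, so a paired test may have been intended. The text does not support that reading: one named test serves both independent subgroups and within-patient change, the comparison is described through two marginal proportions, and the paired/independent distinction is drawn only for means. Even if McNemar was meant, a programmer could not tell.

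The consequences are limited, and this stands. The primary endpoint is descriptive, p-values are exploratory, and under positive correlation the error is conservative. The label changes only in a narrow window; a change from 40% to 50% already gives unpaired p = 0.044, 0.025 and 0.014 at n = 200, 250 and 300. All correlations are assumed.

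Three qualifications to the size also stand.

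- **Smaller samples.** Of the 98 p-values, 18 are caregiver rows and 2 belong to EPQ10 (parents' understanding), which concerns ages 12 to 17. These 20 rest on a paediatric subset of unstated size, so figures for 200 to 300 patients do not apply. At an assumed n = 100 the thresholds would be 13.83 points unpaired and 13.26 to 9.89 paired.
- **Repeated cells.** Items 9 and 10 at Week 12 appear in both 7.1.9 and 7.1.13 (4 repeats). Because the FAS is in essence Week-12 completers, the Week-12 column of 7.1.15 should repeat that of 7.1.13 (6 more). About 88 are distinct.
- **Nominal rate restored.** With no multiplicity control, expected null labels over 98 cells rise from 98 × 0.019 ≈ 1.9 (ρ = 0.3) to 98 × 0.05 = 4.9. That is the rate the SAP states.

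On IGA, it is fair that the tables also print the change in percentages, so the reader still sees the effect. That is a reason to drop the p-values, since they add nothing to it.

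**Conclusion.** Both parts hold. As written, SAP 6.3.1 applies an unpaired test to paired proportions, and the p-values in five tables do not have the stated 0.05 level. The size and direction rest on an assumed positive correlation, under which the error costs power without adding false positives. It can change labels at the interim size, for changes of roughly 7 to 10 points from a 40% baseline, and in a lower and slightly narrower window at 300.

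The IGA part needs no correlation assumption. It follows from the eligibility rule alone, eligibility deviations aside: 12 p-values cannot inform, and the baseline-column p-values in Table 7.2.4.5 do not exist.

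Because the p-values are exploratory and no estimate is affected, this should be corrected but does not threaten the study's main results.

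**What to change.** In SAP 6.3.1, state that within-patient changes in proportions (both category groupings, at Weeks 4, 8 and 12) are tested with McNemar's test, exact when discordant pairs are few, in subjects with both assessments. Report the number of pairs and the paired difference with a 95% confidence interval. Keep chi-square for comparisons between subgroups only. Apply this to the interim as well, since its methods must match the final analysis.

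Delete the p-values from Tables 7.2.4.2 and 7.2.4.6 and from the baseline column of Table 7.2.4.5. Report the IGA proportions at Weeks 4, 8 and 12 with exact 95% confidence intervals.

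The cost is SAP wording, a test option in the programs, and added intervals in the shells; no new data are needed. McNemar uses complete pairs, whereas the SAP uses all available data. At Week 12 the loss should be small, "since patients answering Week 12 survey will have completed all relevant PRO related questions" (SAP section 7). It matters mainly for the unimputed Week 4 and 8 columns of Table 7.1.13.

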### **6.3.2 Study Subjects**

Upon successful recruitment of the study sites, the respective Site Investigators may identify a study coordinator at their clinics. Site Investigators and/or the study coordinator will approach, screen and consent up to ten (10) study-eligible Subjects sequentially within the study enrollment window. The approach may take place during the routine patient visit or via email or phone; upon establishing contact with study Subjects, they will be provided with a description of study objectives and procedures.

In the case of in-person recruitment of study Subjects, Subjects will be screened for study eligibility using the study screener. The Subjects deemed eligible for the study will then be provided with a study informed consent form. The study coordinator or Site Investigator will ensure that Subjects can read the consent form and ask questions, and be given adequate time to consider the benefits/risks associated with participation in the study. An informed consent (with an accompanying assent, if applicable, for pediatric patients) will be obtained from each subject (and parent(s) or legal guardian(s), if applicable) in accordance with applicable regulations prior to participating in any study procedures. Subjects under the age of 18 will assent.

In the case of recruitment of study Subjects via email or phone, study coordinator or Site Investigator will pre-screen the Subjects for study eligibility, and will then contact the subject to describe the study to each subject (and parent(s) or legal guardian(s), if applicable) and give them adequate time to consider the risks associated with participation in the study. The eligible Subjects will be then provided with a weblink to an online screener and electronic consent (e-consent) form. If a Mobile App is used for the purpose of the study data collection from the Subjects, recruited study Subjects will be asked to download the Mobile App; as they log-in an e-consent form may be presented via the App. Subjects will be able to quickly read and provide informed consent (and assent if applicable, for pediatric patients) prior to participating in any study procedures by checking a box next to the statement, "I have read the above statement and I consent to participate in this study" and signing their name(s) along with dating the online form (using their web browser or the study Mobile App).

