## 12.3 General Statistical Procedures

### 12.3.1 Overview

Data from Site Investigators and study Subjects will be combined into one dataset. No site-specific analyses will be conducted. Validated instruments will be scored according to developer guidelines, reporting domain scores and overall summary scores, as appropriate. Home-grown questions/items will be analyzed and reported individually, based on the respective response scales.

Statistical differences in discrete variables will be assessed using a  $\chi^2$  test. Continuous measures will be assessed using the appropriate parametric or nonparametric test. P values  $\leq 0.05$  will be considered significant in all analyses. All statistical analyses will be based on all available data assuming that all missing data are uninformative and will be conducted using appropriate statistical software, such as SAS.

The final study analyses will be conducted after the completion of 12 weeks of data collection for all study Subjects.

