### **12.3.3 Multivariate Analyses**

CFB in key study outcome measures at Week 12 post-index date, and at Weeks 4 and 8 (if applicable) post-index date will be assessed using relevant multivariate analyses, adjusting for subject baseline characteristics and other variables (such as medication adherence) to discern the factors influencing these outcomes, as feasible. Repeated measures analyses with covariates may be used to statistically test the changes/trends for relevant outcome measures over time.

Pearson correlation coefficients may be used to assess the correlation between key outcome measures; this may also inform the consideration of covariates in select multivariate analyses (to reduce multicollinearity).

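### No p-value planned in the SAP allows for clustering of subjects within sites; the four ASIS domain-change t-tests will be too optimistic if change correlates within site (minor)

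*SAP*

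**What the plan says.** Subjects are recruited through practices. Protocol 6.3.2 has each site "consent up to ten (10) study-eligible Subjects sequentially within the study enrollment window". Protocol 12.1 plans about 300 subjects from at most 50 sites; SAP 6.1 plans the same number from at most 40.

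The tests are set in SAP 6.3.1 Overview. For continuous measures, "paired sample t-tests will be used to assess statistical differences for CFB evaluations, while independent sample t-tests will be used" to compare subgroups. A chi-square test is used for subgroup differences in discrete measures and also for "CFB in proportion of patients reporting a particular response to an outcome measure at a particular timepoint", after grouping the top two or bottom two response categories. The SAP names no site effect, GEE, mixed model or cluster-robust variance.

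On status, the SAP says: "Computation of statistical differences will be performed only as an exploratory step (and not for hypothesis testing", given the descriptive nature of the study. It then adds a threshold: "for such exploratory evaluation, P value" at or below 0.05 counts as significant.

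The protocol pools the data (12.3.1 Overview: "No site-specific analyses will be conducted"). Protocol 12.3.3 offers optional models: "Repeated measures analyses with covariates may be used to statistically test the changes/trends". It does not name site as a covariate or random effect, and the SAP does not carry these models forward.

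**The concern.** Subjects at one practice share the clinicians who select them, prescribe for them and assess them, and they share a local patient population. Their outcomes may therefore be more alike than those of subjects from different practices. The t-tests and chi-square tests in the SAP assume that subjects are independent. If within-site correlation is positive, 300 subjects carry less information about an overall mean change than the test supposes. The standard error is then too small and p-values fall below 0.05 too often.

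What is at stake is the precision that the printed p-values imply. The point estimates are not affected.

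**Working it through.** **Inputs.** N = 300 (Protocol 12.1, SAP 6.1). Average subjects per site, m: 300/50 = 6 and 300/40 = 7.5 at the maximum numbers of sites; 10 if every site reaches the cap (300/10 = 30 sites). Alpha = 0.05 (SAP 6.3.1); the SAP does not state sidedness, so two-sided is assumed. The ICC of the change score is not in the documents; 0.02 to 0.10 is assumed. The plan has no sample-size or power figure to reproduce. With ICC = 0 the formula below returns the nominal 0.050.

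**Paired t-tests of overall change.** Table 7.1.10 has four: Symptom, Impact, Emotional Impact and Social Impact.

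- Design effect: DE = 1 + (m − 1) × ICC.
- The naive standard error is too small by a factor of √DE; effective N = 300/DE.
- Real two-sided error = 2 × [1 − Φ(1.96/√DE)].

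| m | ICC | DE | √DE | Effective N | Real error |
|---|---|---|---|---|---|
| 6 | 0.02 | 1.10 | 1.05 | 273 | 0.062 |
| 6 | 0.05 | 1.25 | 1.12 | 240 | 0.080 |
| 6 | 0.10 | 1.50 | 1.22 | 200 | 0.110 |
| 7.5 | 0.02 | 1.13 | 1.06 | 265 | 0.065 |
| 7.5 | 0.05 | 1.325 | 1.15 | 226 | 0.089 |
| 7.5 | 0.10 | 1.65 | 1.28 | 182 | 0.127 |
| 10 | 0.02 | 1.18 | 1.09 | 254 | 0.071 |
| 10 | 0.05 | 1.45 | 1.20 | 207 | 0.104 |
| 10 | 0.10 | 1.90 | 1.38 | 158 | 0.155 |

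The formula takes equal site sizes and all 300 subjects. The Full Analysis Set keeps only subjects with Week 12 survey data (SAP 6.2), so the number per site will be somewhat lower and the effect somewhat smaller.

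**Chi-square tests of change in proportions.** The table shells hold 110 such p-values: 22 in Table 7.1.6.2, 34 in 7.1.9, 18 each in 7.1.13 and 7.1.15, and 6 each in 7.1.18, 7.2.4.2 and 7.2.4.6. Each compares Baseline with a later visit in the same subjects by a test for independent samples. With equal variance at both visits and within-subject correlation r (an assumption), pairing multiplies the true variance by (1 − r) relative to the naive one, and clustering multiplies it by DE:

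- r = 0.3: 0.7 × 1.10 = 0.77 up to 0.7 × 1.90 = 1.33; real error 0.026 to 0.089.
- r = 0.5: 0.5 × 1.10 = 0.55 up to 0.5 × 1.90 = 0.95; real error 0.008 to 0.044.

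The two omissions work against each other, and the sign of the net error is not known in advance.

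**Subgroup t-tests.** These were simulated with N = 300, m = 6 or 10, ICC 0.05 to 0.20 and 8,000 data sets per setting. The real error at nominal 0.05 was:

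- subgroup balanced within site: 0.025 to 0.045 (conservative);
- subgroup random with respect to site: 0.051 to 0.057 (near nominal);
- subgroup fixed by site: 0.080 to 0.244 (inflated).

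The planned subgroups in SAP 6.3.2 are all patient characteristics, so a subgroup fixed entirely by site is an extreme case.

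**The case against.** The strongest reply is that little depends on these p-values. The primary endpoint is analysed descriptively, the secondary endpoint is a single-arm proportion, no power calculation was made, and the SAP rules out hypothesis testing. This stands as a reason to rate the point minor. It does not remove it, because the SAP still sets a significance threshold and prints the p-values.

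A second reply is that the size is unknown. Stable differences between sites cancel in a change score, so the relevant ICC is that of change, and it could be small. That also stands; at an ICC near zero the tests are close to nominal.

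Some stronger readings are tempting, but the documents do not support them:

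- **That every planned p-value is too small.** This holds only for the four paired t-tests, and only if change scores correlate positively within site. The chi-square and subgroup tests can err in either direction.
- **That IGA success and investigator satisfaction are worst affected.** Tables 7.2.4.3, 7.2.4.7 and 7.2.8 carry no overall p-value, and SAP 6.3.1 Summary Statistics lists no standard error or confidence interval. No overall error rate can be quoted for either. Only their subgroup p-values (Tables 7.2.4.8 and 7.2.9) are touched.
- **That one investigator rates all subjects at a site.** SAP 5.3.1 fixes the evaluator per subject, not per site, and Table 7.2.4.1 allows for dermatologists, nurse practitioners and physician's assistants. ASIS and EPQ are answered by subjects or, at ages 9 to 11, by caregivers.
- **That the protocol forbids adjusting for site, or already provides for it.** Ruling out site-specific analyses concerns reporting by site, not the variance. Protocol 12.3.3 would be compatible with a site term but does not mention one.

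**Conclusion.** The point holds as a minor one. The SAP's tests do not account for site, and the design puts an average of 6 to 10 subjects in each. For the four ASIS domain changes, a nominal 5% test has a real error of about 6% to 16%. This rests on an assumed change-score ICC of 0.02 to 0.10, equal site sizes and two-sided testing. For the 110 chi-square change p-values the net direction is uncertain, because the neglected pairing offsets the neglected clustering in part or more than fully. Subgroup p-values may be conservative, near nominal or inflated, depending on how the subgroup is spread over sites.

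**What to change.** In SAP 6.3.1 Overview, compute each change-from-baseline p-value from within-subject differences: the score difference for ASIS domains, and the difference of the top-two or bottom-two indicators for single items and IGA. Test the mean difference with site-clustered robust standard errors. This handles pairing and clustering together. It also works where the baseline proportion is 0% or 100% by entry criterion, as for IGA, where subjects must score 3 or 4.

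Use the same site-clustered variance for subgroup p-values, for example GEE with site as the cluster. An independence working correlation keeps the planned point estimates unchanged. With only some 30 to 50 sites, a small-sample correction to the robust variance is sensible.

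Tables and point estimates stay as planned. Where data are missing and not imputed, state that the change p-value uses subjects with both visits. Site identity appears to be held already, since Table 7.2.1 counts unique sites and SAP sections 9 and 10 refer to Site S01. The cost is a few sentences of SAP text, a little more code, and probably slightly less favourable p-values for ASIS domain change.
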